6.2. Adjustments for Covariates

The study is stratified by baseline HbA1c with country as a block factor; therefore, both stratification factors will be fitted in the corresponding statistical model as fixed effects for the non-HbA1c measurements unless otherwise stated. For HbA1c analysis, the strata of baseline HbA1c will be replaced with the covariate of baseline HbA1c. For other continuous variables other than some safety laboratory measures, a corresponding baseline measure will be added as a covariate.

6.3. Handling of Dropouts or Missing Data

Missing data will be imputed as a sensitivity analysis for the primary and key secondary continuous endpoints using a tipping point approach, and copy reference approach. The reference is from those patients on the same treatment who received rescue medication and/or stopped study medication, but had the measurement for the corresponding endpoints.

For HbA1c target of <7.0% and $\leq 6.5\%$, those who have missing data at Week 18 (Visit 12) or who receive rescue therapy prior to the Week 18 visit will be imputed as not reaching HbA1c target.

Last observation carried forward (LOCF) to impute the missing endpoint data will be used for the non-longitudinal continuous variables such as 6-point self-monitored plasma glucose (SMPG), Homeostasis Model Assessment (HOMA-IR), and HOMA-%B, c-peptide, fasting insulin, and the selected safety laboratory measures.

Any missing component of date and/or time will be imputed following Lilly or dulaglutide compound level standards. For example, the missing day or month could be imputed with the first day of the month, or first month of the year.

If the first dosing date/time is missing, the non-missing randomization date will be used to impute the first dosing date and the time will be placed with 0800 hours. The 0800 hours is the most common first injection time per historical dulaglutide studies. This imputation is only applicable for PK related exposure analysis.

Other imputation may be applied if deemed necessary even after this document is approved. This addition or even change does not require an SAP revision. Rather, those detailed imputation rules will be documented in a separated file such as statistical decision log or track change log.

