## 2. Schedule of Activities

Visit	Screening and Lead-In		Treatment Period										Follow-Up	
	1	2	3	4	5	6	7	8	9	10	11	12	801	ET a
Week of Treatment	-2	-1	0	2	4	6	7	8	9	10	14	18	22	ET
Allowable Deviation (Days)b	±3	±3		-3	-3	-3	±3	±3	±3	+4	±7	±7	±3	
Informed consent	X													
Randomization c			X											
Clinical Assessments														
Medical History	X													
Physical	X													
Height	X													
Weight	X		X	X	X	X	X	X	X	X	X	X	X	X
Vital Signs (3 sitting BP and PR measurements)	X		X	X	X	X	X	X	X	X	X	X	X	X
Electrocardiogram d	X					X		X		X		X		X
Adverse events		X	X	X	X	X	X	X	X	X	X	X	X	X
Concomitant medications	X	X	X	X	X	X	X	X	X	X	X	X	X	X
Review/record hypoglycemic events			X	X	X	X	X	X	X	X	X	X	X	X
Remind patients about 6-point SMPG		X									X			
Record 6-point SMPG values e			X									X		X f
Patient summary												X	X	X
Patient Education and Management														
Dispense study diary, instruct in use		X	X			X				X	X	X		
Review study diary			X	X	X	X	X	X	X	X	X	X	X	X
Return study diary			X			X				X	X	X	X	X
Diabetes management education g		X												
PG meter, SMPG training g		X	X											
Review SMPG values			X	X	X	X	X	X	X	X	X	X	X	X
Injection training g		X	X											
Dispense PG meter/supplies		X	X	X	X	X	X	X	X	X	X	X		
Dispense study drugs and/or injection supplies			X	X	X	X				X	X			
Observe patient inject study drug h			X											

Visit	Screening and Lead-In		Treatment Period										Follow-Up		
	1	2	3	4	5	6	7	8	9	10	11	12	801	ET a	
Week of Treatment	-2	-1	0	2	4	6	7	8	9	10	14	18	22	ET	
Allowable Deviation (Days)b	±3	±3		-3	-3	-3	±3	±3	±3	+4	±7	±7	±3		
Patient Education and Management (concluded)															
Patient returns study drugs and/or injection supplies				X	X	X	X	X	X	X	X	X		X	
Assess study drug compliance i				X	X	X	X	X	X	X	X	X		X	
Laboratory tests															
Serum pregnancy test j	X														
Urine pregnancy test k			X												
Follicle-stimulating hormone test l	X														
Chemistry panel	X											X		X	
Lipid panel (fasting) m			X									X		X	
Urinalysis	X											X		X	
Albumin/creatinine ratio (urine) n	X											X		X	
eGFR (CKD-EPI) o	X											X		X	
Hematology	X											X		X	
Immunogenicity			X			X						X	X	X	

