##### **10.3.3.3. Tertiary/Exploratory Efficacy Endpoints**

The analysis of patients reaching HbA1c target  $\leq 6.5\%$  will use the same model as that for HbA1c target <7.0% described in Section 10.3.3.2.2.

Longitudinal continuous variables such as fasting glucagon will be analyzed using MMRM described in Section 10.3.1. If the normality assumption is violated, appropriate transformation is needed prior to analysis.

Non-longitudinal continuous variables such as 6-point SMPG, HOMA-IR, and HOMA-%B will be analyzed using last observation carried forward (LOCF) by fitting a linear model with pooled country, treatment, baseline HbA1c strata as fixed effect, and corresponding baseline value as a covariate. Data transformation may be applied if data are not normally distributed.

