The analysis of covariance (ANCOVA) as a sensitivity analysis for the primary and secondary continuous efficacy endpoints using the last observation carried forward (LOCF) described in Section 10.3.1 of the protocol H9X-MC-GBGJ(a) will not be used for analyses of secondary continuous efficacy endpoints as the analysis was shown to produce biased results (Lachin 2016) with little inferential value.

For continuous laboratory measurements for safety, an analysis of variance (ANOVA) on ranks will be used with treatment as a fixed effect.

For all continuous measures, summary statistics will include number of patients, mean, SD, median, minimum, and maximum for both the actual and change from baseline values at each scheduled visit for each treatment unless otherwise specified. Least-squares mean (LS mean) and standard errors (SEs) derived from the model will also be displayed for the change from baseline values at each scheduled visit for each treatment. Treatment comparisons will be displayed showing the treatment difference LS mean and the 95% CIs between each dose and placebo, and between each investigational dulaglutide dose and 1.5 mg at the same visit, along with the corresponding p-values.

Summary statistics for categorical measures will include number of subjects and percentages. The percentage of patients achieving target HbA1c <7.0% at Week 18 will be analyzed using a longitudinal logistic regression with repeated measurements with treatment, visit, treatment-by-visit interaction, and baseline HbA1c-by-visit interaction as fixed effects and baseline HbA1c as a covariate. For the analysis of other categorical measures, Fisher's exact test will be used for treatment comparisons, unless 80% of cells have an expected value of at least 5, in which case the Chi-square test will be used unless otherwise stated. Unless otherwise stated, categorical variables will be summarized by sample size, the number of patients and percentages for each treatment group at each visit.

Imputed data may be applied in model-based data analysis, but will not be used in data listing.

The latter will only present the non-imputed raw data including site reported scheduled, site reported unscheduled, or early termination visit data; however, only scheduled visits for the measure of interest ([Appendix 1](#), Table APP1.1) will be included in the summary table and statistical inference unless otherwise stated.

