6.6. Patient Population

Five patient populations are defined for the analyses in this study with detailed information listed in [Table GBGJ.2](#). Unless otherwise specified, listings will include all randomized patients. Efficacy and safety analyses will be conducted in the intent-to-treat (ITT) population. The primary efficacy measure (change from baseline in HbA1c) will also be evaluated in the per protocol (PP) population and Completer set (CS) population.

In all efficacy and hypoglycemia analyses, all data after rescue therapy will be censored unless otherwise stated.

Analyses of safety parameters, except for hypoglycemia events, will be conducted in the ITT population including the post-rescue therapy data.

Table GBGJ.2. Populations for Analyses

Population	Description
Entered	All participants who sign informed consent
Intent-to-treat	All participants who are randomized and take at least 1 dose of study medication for an assigned treatment arm
All randomized population	All patients who are randomized
Per protocol	
All ITT patients who meet all of the following criteria:
 
 • Have no important protocol deviation that could impact the assessment of the primary endpoint; the list of specific criteria is provided in Section 6.15 • At least 75% compliant with study drug administration • Complete the treatment period (18 weeks) • Have a value of the primary efficacy measure at 18 weeks 
Note: the final criteria will be documented in electronic Trial Master File (eTMF).

Completer set	All ITT patients who complete 18 weeks of study drug treatment without rescue therapy

Abbreviation: HbA1c = hemoglobin A1c; ITT = intent to treat.

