6.17. Planned Exploratory Analyses

Some of the planned exploratory analyses are described in Section 6.1. The remaining exploratory exploratory analyses are described in this Section.

The analysis of patients reaching HbA1c target $\leq 6.5\%$ will use the same model as that for HbA1c target $< 7.0\%$ described in Section 6.11.3.

Longitudinal continuous variables such as fasting glucagon will be analyzed using MMRM described in Section 6.1. If the normality assumption is violated, appropriate data transformation is needed prior to analysis.

Non-longitudinal continuous variables such as 6-point SMPG, c-peptide, fasting insulin, HOMA2-IR, and HOMA2-%B will be analyzed using LOCF by fitting a linear model with pooled country, treatment, baseline HbA1c strata as fixed effects and the corresponding baseline value as a covariate. A data transformation may be applied if data are not normally distributed.

The 6-point SMPG consists of measurements before and 2 hours after each of 3 main meals within the same day. Each of the time point of the 6-point SMPG will be analyzed separated.

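### LOCF is the only planned analysis for SMPG, HOMA, C-peptide and fasting insulin, yet with one scheduled post-baseline visit it has only an early-termination value or baseline to draw on

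*SAP*

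**What the plan says.** SAP 6.1 withdraws an LOCF analysis of covariance, stating that it "will not be used for analyses of secondary continuous efficacy endpoints as the analysis was shown to produce biased results", and adds that it has little value for inference. SAP 6.3 and 6.17 keep LOCF for another group. SAP 6.3 says: "Last observation carried forward (LOCF) to impute the missing endpoint data will be used for the non-longitudinal continuous variables such as" 6-point SMPG and the others named here. In 6.17 these variables (6-point SMPG, C-peptide, fasting insulin and the two HOMA indices) "will be analyzed using LOCF by fitting a linear model with pooled country, treatment, baseline HbA1c strata as fixed effects", with the corresponding baseline value as covariate. No other method and no sensitivity analysis is named for them. Protocol 10.3.3.3 has the same LOCF rule for SMPG and HOMA.

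The Schedule of Activities places "Record 6-point SMPG values", fasting insulin and C-peptide at Visit 3, Visit 12 and the ET visit only. A footnote makes the ET profile for SMPG conditional on its having been collected before that visit.

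Two further rules matter. SAP Table APP1.1 gives SMPG, C-peptide and fasting insulin a Visit 12 window of (2, B), where B is the day the patient ends the maintenance phase. SAP 6.6 says: "In all efficacy and hypoglycemia analyses, all data after rescue therapy will be censored unless otherwise stated".

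**The concern.** LOCF needs an earlier post-baseline value to carry, and the schedule provides none for these variables apart from an ET value. An ET value may come from any week. A change from baseline to Week 18 would then mix true Week 18 measurements with values taken after a few injections.

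The mixing need not be even across arms. The 1.5 mg arm starts at its assigned dose and the 4.5 mg arm does not, so an early value means something different in each. SMPG and HOMA are listed in Table GBGJ.1 for comparison with both placebo and 1.5 mg, and the protocol says that its exploratory objectives are there to guide Phase 3 dose selection.

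Rescued patients raise a separate question. Their Visit 12 value is removed, and the SAP does not say whether the baseline value then stands in for it (change of zero) or the patient leaves the analysis.

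**Working it through.** **The plan's own figure.** Protocol 10.1 and SAP 5.2: 75 × (1 − 0.20) = 60 completers per arm, and 38 × 0.80 = 30.4, or about 30 per algorithm. Both reproduce. The documents give no missing-data rate specific to these variables and no rescue rate.

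**What is available to carry.**

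| Variable | Scheduled values | Visit 12 window | What turns an ET value into Week 18 |
|---|---|---|---|
| SMPG | Visit 3, Visit 12, ET if already collected | (2, B) | the window |
| C-peptide, fasting insulin | Visit 3, Visit 12, ET | (2, B) | the window |
| HOMA-IR, HOMA-%B | limited by the insulin or C-peptide sample | not in the table; site-reported visit | LOCF, if applied |

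For the first two rows LOCF itself can add only a baseline value, because the window has already taken the ET value.

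**Dose behind an ET value (Protocol Table GBGJ.2).** In Weeks 0 to 5 the 1.5 mg arm receives 1.5 mg throughout. The 4.5 mg arm receives 0.75 to 3.0 mg. The 3.0 mg arm is below its assigned dose until Week 4 under Algorithm 1 and throughout titration under Algorithm 2. An ET value on Day 15 would still count as Week 18 under (2, B), although the Visit 12 target is Day 127.

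**Rescued patients.** Protocol 5.1 and 8.1.1 keep patients who stop study drug in the trial on rescue treatment. If they complete, they have no ET visit, and their Visit 12 value is censored. Baseline is their only remaining scheduled value.

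**Dilution of one arm's effect.** Let p be the share of patients without a true Week 18 value and f the share of the Week 18 effect already present in the substituted value (f = 0 is baseline carried forward). The arm keeps 1 − p + p·f of its effect, so dilution = p × (1 − f). Only p = 0.20 comes from the plan, as its dropout rate. The other p values and every f are assumptions.

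| p | f = 0 | f = 0.25 | f = 0.50 | f = 0.75 |
|---|---|---|---|---|
| 0.10 | 10% | 7.5% | 5% | 2.5% |
| 0.20 | 20% | 15% | 10% | 5% |
| 0.30 | 30% | 22.5% | 15% | 7.5% |

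**Contrast with 1.5 mg.** Take two active arms with the same true change.
- Equal missingness, unequal f: with p = 0.20 in both, f = 0.75 on 1.5 mg and f = 0.50 on 4.5 mg, the false difference is 0.20 × (0.75 − 0.50) = 0.05 of the common change.
- Unequal missingness, baseline carried: the false difference is the difference in p. For 25% against 15% it is 0.10 of the common change; for 30% against 10% it is 0.20.

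**Simulation.** Settings: 75 per arm, 6,000 runs, SD 1, values missing completely at random, baseline carried forward.
- True difference −0.83 SD (the HbA1c planning ratio 1.0/1.2, borrowed only as a scale), 20% missing in both arms: mean estimate −0.665, 95% interval coverage 81%.
- Equal true change of −1 SD: 25% against 15% missing gave a false 0.10 SD and 10% rejection; 30% against 10% gave 0.20 SD and 25% rejection.
- Using only observed values, the estimates were unbiased and rejection in the equal-change cases was about 5%. That result depends on the completely-at-random assumption.

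**The case against.** Several stronger readings are tempting, and the documents do not support them.

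- *LOCF contradicts the missing-at-random statement.* It does not. SAP 6.1 makes both missing at random and the absence of imputation subject to other provisions, and 6.3 and 6.17 are such provisions. This is a declared exception.
- *SAP 6.1 bans LOCF everywhere.* The withdrawal is worded for secondary continuous efficacy endpoints, which have several visits and a repeated-measures model. A repeated-measures model offers little with a single post-baseline visit. The reason given, bias, is nonetheless general, and no reason is offered for the exception.
- *LOCF is what relabels ET values.* For SMPG, C-peptide and insulin the window does so. Only for HOMA could it be LOCF.
- *Baseline will be carried forward.* The SAP is silent. If baseline is not carried, LOCF adds almost nothing beyond the window.
- *GI dropout produces many early ET values at high doses.* Protocol 3.2 reports 5 of 33 patients (15%) stopping early for GI events at 3.0 mg or more, but patients who stop drug for adverse events are required to stay in this trial. They reach the problem through rescue censoring. The documents give no dropout rates by dose.

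Protocol 5.4 also puts the maximum glucose-lowering effect at about 2 weeks after initiation, which favours higher f for glucose measures. That helps less where the dose at ET is below the assigned one.

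The strongest remaining objection concerns the replacement. An analysis of observed Week 18 values compares patients who stayed and were not rescued. If missingness depends on tolerability or response beyond baseline, that analysis is selective too.

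**Conclusion.** The point holds in limited form. The SAP keeps, as the sole analysis for five variables, a method that it calls biased elsewhere. The visit schedule leaves that method only an ET value or baseline, and the (2, B) window has the same effect for three of the variables before LOCF acts. The rule for rescued patients is undefined.

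The size is uncertain. At 20% missing the dilution of an arm's effect runs from 5% (75% of the effect reached) to 20% (none reached). Apart from the planned dropout rate, these inputs are assumptions. The 20% figure also requires baseline to be carried, or an ET value that shows no effect.

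The weight is low to moderate. SMPG and HOMA are tertiary/exploratory, and C-peptide and fasting insulin are not listed in Table GBGJ.1. The primary HbA1c model does not use LOCF, and the interim efficacy criteria in SAP 6.16.2.2 rest on HbA1c and body weight.

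**What to change.** 1. Delete LOCF for these five variables from SAP 6.3 and 6.17, and for SMPG and HOMA from Protocol 10.3.3.3. If the protocol is not amended, record the change and its justification in the SAP, as SAP 6.1 allows.
2. In Table APP1.1, replace (2, B) for SMPG, C-peptide and fasting insulin with a true Week 18 window, such as the (100, B) already used for HbA1c and fasting glucose, and add HOMA with the same window. On-schedule profiles still fit: Day 127, less 7 days of visit deviation and 7 days for SMPG collection, is Day 113.
3. Fit the model already planned (pooled country, treatment, HbA1c stratum, baseline) to values in that window that the rescue rule leaves in, under missing at random.
4. Show ET values descriptively, with the time at which they were taken.
5. State that baseline is not carried forward.

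Deleting the LOCF text alone would leave the relabelling by the window in place, so items 1 and 2 belong together.

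The cost is wording, plus up to about 20% fewer values from the planned dropout and a further loss from rescue censoring. At 60 instead of 75 per arm and the same SD, intervals widen by a factor of √(75/60) = 1.12. The SAP should also name the selection risk described above. The model conditions on baseline but, unlike the repeated-measures model for HbA1c, has no intermediate visits to inform the missing values.

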HbA1c	X		X			X				X		X	X	X	
Glucose (fasting) m			X			X				X		X	X	X	
Pancreatic amylase, lipase	X		X			X						X	X	X	
Serum insulin (fasting) m			X									X		X	
C-peptide			X									X		X	
Plasma glucagon (fasting) m,p			X			X						X		X	
Calcitonin	X		X									X		X	
Pharmacogenetic			X												
Nonpharmacogenetic biomarker (plasma and serum)			X		X	X						X		X	
PK samples															
PK samples			X q	X r	X q	X s					X t		X u	X u	X u

Abbreviations: BP = blood pressure; CKD-EPI = Chronic Kidney Disease-Epidemiology; ECG = electrocardiogram; eGFR = estimated glomerular filtration rate; ET = early termination; HbA1c = hemoglobin A1c; OAM = oral antihyperglycemia medication; PG = plasma glucose; PK = pharmacokinetic; PR = pulse rate; SMPG = self-monitored plasma glucose.

- a Patients who are unable or unwilling to continue in the study because of an adverse event or any other reason will perform an ET visit as their final study visit. If the patient is discontinuing during an unscheduled visit, that visit should be performed as the ET visit. If the patient is discontinuing during a scheduled visit, that visit should be considered the ET visit.
- b The visit date is determined in relation to the date of the randomization visit ( $\pm$  the allowed visit window).
- c Baseline assessments must be completed before processing in the interactive web-response system (IWRS).
- d ECGs will be performed in triplicate. ECGs occurring on visits with PK collection should be measured at least 30 minutes prior to obtaining the sample for PK measurement.
- e 6-point SMPG consists of measurements before and 2 hours after each of 3 main meals within the same day. These SMPG profiles are collected by the patient within 1 week prior to the assigned visits.
- f If performed prior to visit.
- g All training should be repeated as needed to ensure patient compliance.
- h Patients should administer their first dose of study drug at the end of this visit, after other study procedures and randomization. Patients will be encouraged to administer their weekly dose of study drug in the clinic, when possible, at subsequent visits.
- i Study drug compliance will be reviewed for the time period from Visit 4 to Visit 12 and entered in the eCRFs at Visit 6, Visit 10, Visit 11, and Visit 12 for the interval after the previous compliance entry.

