- j A serum pregnancy test will be performed at Visit 1 for women of childbearing potential only.
- k A urine pregnancy test will be performed at Visit 3 with the result available prior to randomization and first injection of study drug for women of childbearing potential only. Additional pregnancy tests may be performed at the investigator's discretion during the study.
- l Follicle-stimulating hormone test performed at Visit 1 for postmenopausal women at least 50 years of age with an intact uterus, not on hormone therapy, and who have had spontaneous amenorrhea for more than 6 months and less than 12 months. After Visit 1, additional tests may be performed at the investigator's discretion during the study.
- m For Visit 3, Visit 6, Visit 10, Visit 12, Visit 801, and the ET visit, patients should be reminded to report to the site in a fasting condition, after a period of approximately 8 hours without eating, drinking (except water), or any significant physical activity and before taking their OAMs (if used).
- n Urinary albumin and creatinine are measured; the ratio is calculated.
- o The CKD-EPI equation will be used by the central laboratory to estimate and report eGFR. Values that are  $<60$  mL/min/1.73 m^2 at Visit 1 must be retested at Visit 2. If the highest of the 2 values is lower than the cutoff value for discontinuation of metformin per country-specific label (for example,  $<45$  mL/min/1.73 m^2 or  $<60$  mL/min/1.73 m^2), the patient will be discontinued from the trial prior to randomization. After randomization (Visit 3), values that are  $<60$  mL/min/1.73 m^2 must be first confirmed on a retest before any protocol-required treatment adjustment is implemented.
- p Collect sample in P800 tube. Aliquot samples, 1 for glucagon and the remainder for nonpharmacogenetic biomarker.
- q PK samples at Visit 3 and Visit 5 should be collected 1-24 hours post-injection of study drug.
- r PK sample at Visit 4 should be collected immediately prior to administration of study drug.
- s PK sample at Visit 6 should be collected 5-7 days (120-168 hours) post-injection of Week 5 study drug or just pre-injection of Visit 6 study drug.
- t PK sample at Visit 10 should be collected 1-4 days (24-96 hours) post-injection of Visit 10 study drug.
- u PK samples at Visit 12, Visit 801, and the ET visit can be collected at any time during the visit.

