### **Study Period II (Treatment Period):**

#### **Randomization (Visit 3)**

At Visit 3, patients will perform study procedures that are required prior to randomization.

Patients who continue to be eligible will then be randomized in a 1:1:1:1 ratio to 1 of the treatment arms: (1) dulaglutide 4.5 mg, (2) dulaglutide 3.0 mg, (3) dulaglutide 1.5 mg, or (4) placebo. Within each of the investigational dulaglutide dose (3.0 mg and 4.5 mg) arms, patients will be randomly assigned in a 1:1 ratio to 1 of the titration algorithms (Algorithm 1 or Algorithm 2). Immediately after randomization, the patient will inject the first dose of study drug at the study site. The Visit 3 pharmacokinetics (PK) sample must be collected 1-24 hours after the patient has injected study drug for the first time.

Following randomization, patients will participate in an 18-week treatment period that consists of a 6-week titration phase followed by a 12-week maintenance treatment phase at the final dosage.

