## 9.5. Pharmacokinetics

Blood samples for determining plasma concentrations of dulaglutide, associated with time from dose, will be obtained at selected visits from all patients in accordance with the Study Schedule and at ET (see Schedule of Activities [Section 2]). However, only samples from patients assigned to treatment with dulaglutide will be analyzed for drug concentrations.

Timing of PK blood draws have been optimized for sparse sampling using a standard PK optimal sampling approach. Pharmacokinetic samples will be drawn to include a range of sampling time windows (predose, and 1-24 hours, 24-96 hours, and 120-168 hours postdose) spread over several clinic visits. For the ET visit, a sample may be drawn at any time during the visit. The study has been designed so that, where possible, each immunogenicity sample will be accompanied by a PK sample in the same visit. At visits where ECG measurements are taken, these should be accompanied by a time-matched PK sample within 30 minutes (before or after), during the same visit.

At the visits and times specified in the Schedule of Activities (Section 2), venous blood samples of approximately 4 mL each will be collected to determine the plasma concentrations of dulaglutide.

Instructions for the collection and handling of blood samples will be provided by the sponsor. The actual date and time (24-hour clock time) of each sampling and all study drug doses must be clearly recorded.

Drug concentration information that would unblind the study will not be reported to investigative sites or blinded personnel until the study has been unblinded.

Bioanalytical samples collected to measure investigational product concentration will be retained for a maximum of 1 year following last patient visit for the study.

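### A missing first-dose time is set to 08:00 without reference to the patient's own randomization, so the imputed dose can precede randomization and mistime the Visit 3 PK sample

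*SAP*

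**What the plan says.** SAP 6.3 (Handling of Dropouts or Missing Data) covers a missing first dosing date or time: "the non-missing randomization date will be used to impute the first dosing date and the time will be placed with 0800 hours". Its reason is that "The 0800 hours is the most common first injection time per historical dulaglutide studies", and it restricts the rule: "This imputation is only applicable for PK related exposure analysis".

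The protocol fixes where the first dose falls within Visit 3. Footnote h to the Schedule of Activities says "Patients should administer their first dose of study drug at the end of this visit, after other study procedures and randomization", and Section 5.1 says "Immediately after randomization, the patient will inject the first dose of study drug at the study site". Footnote c requires the baseline assessments to be finished before the IWRS transaction.

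On sampling, footnote q says "PK samples at Visit 3 and Visit 5 should be collected 1-24 hours post-injection of study drug". On data capture, Protocol 9.5 says "The actual date and time (24-hour clock time) of each sampling and all study drug doses must be clearly recorded".

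**The concern.** The SAP takes one clock time from other studies and applies it to every patient whose first-dose time is missing. It does not use the order of events that this protocol lays down. Randomization is a lower bound on the dose time, and the recorded Visit 3 PK sample time is an upper bound. The rule uses neither, and nothing in SAP 6.3 stops an imputed dose from landing before randomization.

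The value at risk is the elapsed time of the Visit 3 concentration. Visits 3 and 5 are the only visits sampled 1-24 h after injection, and only Visit 3 follows the first dose. Dosing times feed the PK analysis (SAP 6.13.1), and characterizing PK and its relation to safety and efficacy is a secondary objective. An error of an hour or more matters most, in relative terms, for a sample drawn soon after the injection.

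**Working it through.** **The plan's own figure.** The 08:00 value cannot be reproduced, because the historical injection times are not in the documents.

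**Inputs from the documents.** Imputed dose time: 08:00 on the randomization date (SAP 6.3). Order of events: Visit 3 procedures, randomization, injection (Schedule of Activities, footnotes c and h; Protocol 5.1). Sampling window: 1-24 h after injection (footnote q). Patients whose samples are assayed: the dulaglutide arms only (Protocol 9.5), about 3 × 75 = 225 (Protocol 10.1).

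**Assumed input.** The actual clock time of the injection, which the documents do not give. It is ranged below.

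**Formula.** Error in time since dose = (sample time − 08:00) − (sample time − actual dose time) = actual dose time − 08:00. The error in hours does not depend on when the sample is drawn.

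| Assumed injection | Error | True 1 h analysed as | True 4 h as | True 12 h as | True 24 h as |
|---|---|---|---|---|---|
| 07:00 | -1 h | 0 h | 3 h | 11 h | 23 h |
| 08:00 | 0 h | 1 h | 4 h | 12 h | 24 h |
| 09:00 | +1 h | 2 h | 5 h | 13 h | 25 h |
| 10:00 | +2 h | 3 h | 6 h | 14 h | 26 h |
| 11:00 | +3 h | 4 h | 7 h | 15 h | 27 h |
| 12:00 | +4 h | 5 h | 8 h | 16 h | 28 h |

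For an injection at 10:00-12:00, the relative error is 2/1 to 4/1 (200% to 400%) for a sample at 1 h and 2/24 to 4/24 (8% to 17%) for one at 24 h. A compliant 24 h sample would then appear to lie outside its window. For an injection at 07:00, a 1 h sample would be analysed as drawn at the moment of dosing.

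**Which sample is sensitive.** The Week 2 sample is nominally 14 × 24 = 336 h after the first dose. The same 2 to 4 h is 2/336 to 4/336, or 0.6% to 1.2%. The problem is confined in practice to the Visit 3 concentration.

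**Consistency with the protocol.** The injection cannot precede randomization. If a patient is randomized after 08:00, an imputed dose at 08:00 contradicts the protocol's sequence, and the error is positive by at least the gap between 08:00 and randomization. If the injection was before 08:00, the error is negative.

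**Patients affected.** No missing rate is given. At assumed rates of 1%, 5% and 10% of 225, the number is 2.25, 11.25 and 22.5, or about 2, 11 and 23 patients.

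**The case against.** The strongest reply is that 08:00 has an empirical basis and any alternative hour is a guess. Visit 3 is a fasting visit ("patients should be reminded to report to the site in a fasting condition"), which suggests a morning attendance, but no clock time is given for the visit, the randomization or the injection. The historical studies' visit flow is not described either. They may also have dosed on site after randomization, in which case 08:00 already reflects that sequence. This stands. A reader might infer from end-of-visit dosing that the imputed elapsed time is hours too long, or that the error always runs in one direction. The documents support neither reading.

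The second reply is that the problem is largely prevented at source. Site staff observe the Visit 3 injection, patients record the time of every injection in the diary, and Protocol 9.5 requires clock times for doses and samples. The rule should seldom be needed. This also stands, and it limits the importance of the point.

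The third reply is that PK/PD details belong to a separate plan (SAP 6.12), and that SAP 6.3 lets imputation rules change through a decision log. Either could correct the rule, but neither is shown to do so, and the 08:00 derivation is written in this SAP.

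The fourth reply is that no effect on exposure estimates has been shown. That is correct. The population PK analysis pools sparse samples over several visits, and a few mistimed Visit 3 samples may not move any estimate. A reader might infer biased exposure-response results, but the documents do not allow that to be calculated.

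**Conclusion.** The point holds as a minor defect of the imputation rule. A fixed time from other studies ignores the patient-level bounds that this protocol's own sequence provides. For anyone randomized after 08:00 it yields a dose before randomization and too long an elapsed time at the Visit 3 PK sample. The +2 to +4 h figure rests wholly on the assumed 10:00-12:00 injection. The reach is narrow: patients with a missing first-dose time, one sample each, in the PK exposure analysis only. The primary and secondary efficacy analyses are untouched.

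**What to change.** Replace the 08:00 sentence in SAP 6.3 with an ordered rule:

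1. If the first-dose time is missing, use the patient's own randomization time, provided the IWRS data hold one. SAP 7.1 says that IWRS data are loaded for the study but does not mention a time stamp, so this is an assumption to confirm.
2. Otherwise use the time of the last recorded pre-dose procedure or sample at Visit 3.
3. In either case, require the imputed dose to be no earlier than randomization and before the recorded Visit 3 PK sample time. Where no randomization time is held, the last pre-dose time serves as the lower bound.
4. If no such time exists, exclude that patient's Visit 3 concentration from the PK analysis, or flag it and run the analysis with and without it.

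Report how many first-dose times were imputed. The cost is a short change to SAP 6.3, one derivation line, and possibly the loss of a few Visit 3 concentrations.
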